Dronabinol (marinol) is an FDA approved, synthetic, orally active cannabinoid that has been shown to be effective for appetite stimulation and safe for chronic use at doses up to 210 mg per day, although after dosing of 210 mg per day for 16 days a withdrawal syndrome was described with abrupt discontinuation. Doses of 2.5-20 mg per day are used for appetite stimulation and antiemetic indications. Doses of 0.5 mg/kg body weight reliably produce intoxication (easy laughing, elation and subjective heightened awareness)

II. SPECIFIC AIMS

Aim 1. Assess the effects of THC intoxication using the medication dronabinol (synthetic THC) on resting state and task-based activation in the prefrontal cortex (PFC), as well as on neurocognitive task performance and correlations between these measurements and clinical signs of intoxication.

Aim 2. Investigate at which doses of dronabinol an effect on neurocognitive task performance or an effect on PFC activity can be observed.

Aim 3. Examine potential interaction following co-administration of THC with oral ethanol exposure in healthy volunteers.

Before enrolling patients in the dronabinol trial, we will enroll 20 participants in Phase 0, in order to pilot the cognitive tasks in order to determine which tasks optimally activate the PFC. In Phase 0, participants will undergo one hour-long fNIRS testing session without taking a dronabinol capsule. Inclusion criteria will be identical to Phase 1, Phase

2 and Phase 3, EXCEPT that participants will not be required to be regular marijuana users.

III. PARTICIPANT SELECTION

Inclusion Criteria

General (Phase 2A, 2B 3)

1. Men and women aged 18-55 years, inclusive; (for Phase 2B: men and women aged 21-55 years, inclusive)
2. Competent and willing to provide written informed consent;
3. Able to communicate in English language.
4. Regular, at least monthly, marijuana use, confirmed by positive urine screen for THC

Additional Inclusion Criteria For Phase 2B:

5. Past consumption of at least two alcoholic beverages in one occasion.
6. Past co-consumption of alcohol and THC at least once in lifetime with no serious adverse effects.
7. Weigh more than 100 lbs.

Exclusion Criteria:

General (Phase 2A, 2B 3)

1. Any unstable, serious medical illness, or cardiovascular disease or events.
2. New or unstable psychiatric symptoms, schizophrenia, or bipolar I disorder,
3. Diabetes, cirrhosis, renal failure, Hepatitis C, HIV,

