participants will also provide a urine sample which will be tested for drugs and pregnancy (if applicable) to ensure participants are positive for THC. Participants are trained on the driving simulator computer tasks. If participants are determined to be eligible, they will be scheduled for the following two visits. In a double-blind, placebo-controlled, random order cross-over study of single dose THC (dronabinol) at physician determined doses of 10-80mg, participants will receive THC capsules or identical placebo on two separate study visits, randomized for order. The MGH research pharmacy will generate a blinded randomization code for order of dosing and will dispense blinded drug in the dose ordered and identical placebo for use on separate study days. In order for a complete washout of effects, and to minimize the effect of repeat testing for the neuropsychology tasks, study visits must be at least 1 week apart. On each study day, participants will have a light standardized breakfast after overnight fast and sleep. They will be asked not to deviate from normal behaviors (e.g. if they drink caffeinated beverages or smoke cigarettes in the mornings, they will be asked to do so on the study day so that no symptoms of caffeine or nicotine withdrawal will appear during the scanning period. On each study day, participants will undergo baseline fNIRS testing (see above “Cognitive Tasks during FNIRS testing”), substance use history interview (timeline follow back), two sets of baseline vital signs, a driving simulator computer task refresher, and several questionnaires (HADS, URGE, PSQI, CWS). Dronabinol or placebo will be administered once morning procedures are complete, after which point heart rate, blood pressure, and responses to DEQ and BAES questionnaires will be monitored at 20 minute intervals. The second fNIRS session will be conducted at approximately 90 minutes post dose, followed by driving simulator computer tasks. A field test of sobriety will be conducted immediately following the second fNIRS assessment. The third fNIRS session will be conducted at approximately 220 minutes post dose, prior to participant discharge. See Below for schematic:

Subjects who participated in Phase 1 will be eligible for Phase 2, but enrollment in Phase 1 is not a requirement for Phase 2. Therefore, new subjects who have not completed Phase 1 will also be eligible for Phase 2.

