Using Imaging to Assess Effects of THC on Brain Activity (fNIRS)

Statistical Analysis Plan

The fNIRS Team

Version 1

First version: 4/29/2022

Latest version: 4/29/2022

ClinicalTrials.gov ID: NCT03655717

Unique protocol ID: 2015P001516

U.S. NIH Grant/Contract Award Number: R42DA043977

Table of contents

Table of contents	2
Glossary	3
Study Design	4
Participants.....	4
Analytic Approach.....	5
Primary Outcomes.....	5
Statistical Model	5
Covariates	6
Missing Data.....	6
Sample Size Determination	7
Software.....	8
References	9

Glossary

Abbreviation	Label
ETOH	Alcohol
FDA	Federal Drug Administration
fNIRS	Functional near-infrared spectroscopy
HbO	Oxygenated hemoglobin
PFC	Pre-frontal cortex
THC	Tetrahydrocannabinol

Study Design

This study will assess the effects of THC intoxication using dronabinol (synthetic THC) on the HbO signal during resting state and task-based activation in the prefrontal cortex (PFC), resting state connectivity, neurocognitive task performance, clinical signs of intoxication, and correlations between these measurements. Participants will be given up to 80 mg of dronabinol, an FDA-approved synthetic form of THC that is used to treat loss of appetite that causes weight loss in people with AIDS. THC is the principle psychoactive drug in marijuana. The study will be conducted in regular cannabis users who present at the screening visit with a positive urine screen for THC metabolites. Data will be collected over two phases:

- Phase 2A is a randomized, double-blind, placebo-controlled, study of effect of dronabinol vs placebo. This phase will investigate the effect of THC on fNIRS brain signature and its association with self-reported intoxication, laboratory measures of impairment, and the gold-standard behavioral field test of driving impairment used by law enforcement.
- Phase 2B is a randomized, double-blind, placebo-controlled, 2 by 2 crossover study of effect of dronabinol, ethanol, and combined dronabinol and ethanol on brain activation and connectivity as measured by fNIRS. Phase 2B will examine potential interaction between THC and alcohol following co-administration of THC with oral ethanol exposure in healthy volunteers.

Participants

Participants will be 150 adults who use marijuana at least monthly (aged 18-55) will be recruited to participate in this study.

Analytic Approach

Primary Outcomes

The primary outcomes for the study will be...

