1. The mean HbO level averaged over the duration of the N-back task scan (approximately 2938 samples taken over 376 seconds in 128 millisecond intervals).
2. The mean HbO level averaged over the duration of the resting state scan (2814 samples taken over 360 seconds in 128 millisecond intervals).

Mean HbO levels for both outcomes will be determined over (a) four conditions administered over separate visits about a week apart (where participants could be dosed with placebo, THC only, ETOH only, or both THC and ETOH), and (b) two scans per condition: A scan prior to and approximately 100 minutes after being dosed. Higher HbO levels indicate a greater degree of neural activity in the PFC regions of the brain.

Statistical Model

We will analyze both primary outcomes using a multi-level linear regression model with subject-varying intercepts estimated via maximum likelihood. The key exposures are whether a person was dosed with placebo, THC, ETOH, or the combination of THC and ETOH. Table 1 lists the numeric coding used to test our planned contrasts. All terms will be coded as 0 for pre-dose scans, as no combination of drugs will have been administered.

Table 1: Design matrix for testing key exposures

Scan	Dose	Main effects		Interaction THC x ETOH
		THC	ETOH	
Post-dose	Placebo	0	0	0
	THC	1	0	0
	ETOH	0	1	0
	THC + ETOH	1	1	1

Statistical significance for each contrast will be determined via a non-parametric bootstrap procedure for robustness. First, each subject's set of completed condition (placebo, THC, ETOH, THC + ETOH) will be randomly shuffled across their set of visits. Second, the shuffled data will be refit with the multi-level model, and coefficient estimates will be obtained for the key exposures. Third, the prior two steps will be repeated 10,000 times, providing a null distribution to compare the observed coefficient estimates against. The p-values for the key exposures will be estimated as $P(|o| < |s_i|)$, where o is the observed coefficient, and s_i is the i th coefficient from the shuffled data. For each outcome there will be 3 p-values (the main effects of THC and ETOH and their interaction). The total set of 6 p-values will be adjusted for multiple comparisons using the Benjamini-Hochberg method (Benjamini & Hochberg, 1995). An adjusted p-value < 0.05 will indicate a statistically significant effect of either THC, ETOH, or their interaction on neural activity in the PFC.

Covariates

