We will include two sets of covariates in our model. First, we will include a dummy-coded contrast comparing pre-dose scans (coded as 0) to post-dose scans (coded as 1). Second, we will include covariates adjusting for visit order. The referent will be the first visit (coded as -1), and we will include three terms for the second, third, and fourth visit (coded as 1 for the given visit and 0 otherwise). All terms will then be converted to z-scores.

Missing Data

We will only include data from complete visits with both pre-dose and post-dose scans. Participants with no complete pairs of pre and post-dose scans for any conditions will be excluded from the analyses. Missingness will be naturally handled by the multi-level modeling approach, as the higher order terms governing the random effects provide shrinkage and information even in the presence of missing cases (Baayen, Davidson, & Bates, 2008).

Sample Size Determination

Sample size was pre-specified in our grant application. Since no prior studies have attempted to predict impairment using fNIRS measurements, we did not have an effect estimate with which to determine sample size. In order to maximize the chance that standard methods could detect an effect of intoxication on PFC activation patterns with the N-Back task, we collected as many scans as possible with the R42 grant funds allotted.

Software

All analyses will be done using the statistical software R (version 4.1.1; R Core Team, 2021) and integrated development environment RStudio (version 2020.9.0.351; RStudio Team, 2021). Data will be prepared using the R packages 'dplyr' (version 1.0.7; Wickham, François, Henry, & Müller, 2021). Models will be fit using the R package 'lme4 (version 1.1-27.1; Bates, Maechler, Bolker, & Walker, 2015).

References

Baayen, R. H., Davidson, D. J., & Bates, D. M. (2008). Mixed-effects modeling with crossed random effects for subjects and terms. *Journal of Memory and Language*, 59 (4), 390-412.
<https://doi.org/10.1016/j.jml.2007.12.005>

Benjamini, Y., & Hochberg, Y. (1995). Controlling the false discovery rate: a practical and powerful approach to multiple testing. *Journal of the Royal Statistical Society: Series B (Methodological)*, 57 (1), 289-300. <https://doi.org/10.1111/j.2517-6161.1995.tb02031.x>.

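### One shuffle of all four condition labels serves as the null for every coefficient, so the THC x ETOH interaction test becomes conservative, and can lose power, once either drug has an effect

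*SAP*

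**What the plan says.** The SAP's Statistical Model section fits a random-intercept model with the Table 1 coding (THC, ETOH and their product, all zero before dosing). It then states: "Statistical significance for each contrast will be determined via a non-parametric bootstrap procedure for robustness". In the first step each subject's "set of completed condition (placebo, THC, ETOH, THC + ETOH) will be randomly shuffled across their set of visits". In the second, "the shuffled data will be refit with the multi-level model, and coefficient estimates will be obtained for the key exposures". These steps are repeated 10,000 times, "providing a null distribution to compare the observed coefficient estimates against". The p-value is the proportion of shuffled coefficients larger in absolute value than the observed one. The coefficients are not studentised.

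The same refits therefore supply the null for all three coefficients on each of the two outcomes. Benjamini-Hochberg is then applied to the six p-values. Neither document describes a restricted or contrast-specific null.

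The interaction is not a side analysis. The SAP's Study Design section says: "Phase 2B will examine potential interaction between THC and alcohol following co-administration of THC with oral ethanol exposure in healthy volunteers". Aim 3 of the protocol reads: "Examine potential interaction following co-administration of THC with oral ethanol exposure in healthy volunteers".

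**The concern.** Shuffling the whole condition label imposes the joint hypothesis that placebo, THC, ETOH and the combination all have the same mean. That is a sound null for asking whether anything differs. The interaction hypothesis is narrower: it asks whether the combination departs from the sum of the two drug effects, whatever those effects are.

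If THC or ethanol changes HbO, the shuffle scatters those changes at random over the labels, where they act as added noise. The interaction null becomes too wide and its p-value too large on average. The same happens to each drug's test when the other drug works.

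At stake is power on Phase 2B's own question. A non-significant interaction also becomes harder to read, because the penalty grows as the drugs become more active.

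**Working it through.** **Inputs.** From the SAP: the shuffle, the unstudentised coefficients, the Table 1 coding and the 0.05 level. The SAP gives no power, effect size or SD ("we did not have an effect estimate with which to determine sample size"), so there is no plan figure to reproduce. Assumed: residual SD σ = 1; THC effect a, ETOH effect b and interaction i in units of σ; n = 50, 75 or 100 complete Phase 2B subjects (the SAP gives 150 overall and no phase split).

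**Step 1: true standard error.** With complete data and all drug terms zero before dosing, the interaction estimate is the mean over subjects of post-dose (both − THC − ETOH + placebo). Its SE is √(4σ²/n) = 2σ/√n.

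**Step 2: SD under the shuffle.** The weights (1, −1, −1, 1) sum to zero and their squares sum to 4. Each subject's shuffled contrast therefore has variance 4 times the within-subject variance of the four values, which averages σ² + V. V is the variance (divisor 3) of the cell means 0, a, b, a+b+i. The null SD is (2/√n)·√(σ² + V), too wide by k = √(1 + V/σ²). With i = 0, V = (a² + b²)/3. The sample size cancels.

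**Step 3: true size of the interaction test at nominal 0.05** = 2Φ(−1.96k), with i = 0.

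| Both main effects | k | Size, formula | Size, simulation |
|---|---|---|---|
| 0 | 1 | 0.050 | 0.050 |
| 0.25σ | 1.021 | 0.045 | 0.044 |
| 0.5σ | 1.080 | 0.034 | 0.032 |
| 1σ | 1.291 | 0.011 | 0.009 |
| 1.5σ | 1.581 | 0.002 | 0.002 |

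The simulation used 75 complete subjects, four balanced sequences, subject and residual SD 1, the SAP coding with post-dose and visit terms, and 3,000 datasets of 399 shuffles.

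For the THC test with no THC effect, k = √(1 + b²/3). Ethanol at 0.5σ gives k = 1.041 and size 0.041; at 1σ, k = 1.155 and size 0.024.

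**Step 4: power at unadjusted 0.05** = Φ(|i|√n/(2σ) − 1.96k). Example with n = 75, i = +0.65, a = b = 0.5: the cell means are 0, 0.5, 0.5, 1.65, so V = 0.489 and k = 1.220. Then 0.65 × 8.660/2 = 2.815 and 2.815 − 1.96 × 1.220 = 0.42, giving power 0.66. A correctly calibrated test (k = 1) gives Φ(0.855) = 0.80.

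| n | i | Correct test | Mains 0.25σ | Mains 0.5σ | Mains 1σ |
|---|---|---|---|---|---|
| 50 | +0.65 | 0.63 | 0.54 | 0.46 | 0.27 |
| 75 | +0.65 | 0.80 | 0.73 | 0.66 | 0.46 |
| 100 | +0.65 | 0.90 | 0.85 | 0.81 | 0.63 |
| 75 | −0.65 | 0.80 | 0.79 | 0.79 | 0.71 |

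Simulated power at n = 75 with mains 0.5σ and 1σ was 0.68 and 0.45 for +0.65, and 0.78 and 0.69 for −0.65.

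**Step 5: after Benjamini-Hochberg.** A separate simulation used 150 complete subjects, i = +0.46σ and an assumed correlation of 0.5 between outcomes, with 250 datasets (simulation error about 0.03). It compared the SAP shuffle with the same shuffle after removing the fitted main effects. Power was 0.65 against 0.71 (mains 0.2σ), 0.70 against 0.81 (0.5σ), 0.47 against 0.81 (1σ) and 0.08 against 0.81 (2σ).

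**Step 6: if Phase 2A visits are pooled.** Shuffled ETOH labels can fall only in Phase 2B visits, so a real ethanol effect moves the ETOH null off zero. With an ETOH effect of 0.4σ, its centre is +0.042 (50 subjects in 2A, 100 in 2B), +0.065 (75/75) or +0.089 (100/50).

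**Step 7: alternatives, same simulation as Step 3.** Freedman-Lane had size 0.048 to 0.053 and power 0.79 to 0.82 at ±0.65σ. Sign-flipping had size 0.048 to 0.052 and power 0.78 to 0.80. THC response may well vary between subjects, since Phase 2A, whose dosing Phase 2B follows, gives "single dose THC (dronabinol) at physician determined doses of 10-80mg". With a between-subject SD of THC response of 0.5σ or 1σ (mains 0.5σ), size was 0.024 or 0.015 for the SAP shuffle, 0.041 or 0.027 for Freedman-Lane, and 0.045 or 0.052 for sign-flipping.

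**The case against.** The strongest reply is that this is a possible loss of efficiency of unknown size. The shuffle is valid when no drug works, it creates no false-positive interactions, and nothing in the documents shows that the drug effects are large enough to matter. That is correct. It limits the seriousness of the point but does not remove the miscalibration.

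Several narrower points also stand:

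- Part of the loss comes from the interaction itself. With both main effects zero and i = +0.65σ, V = 0.106 and k = 1.051, so power at n = 75 is already 0.77 rather than 0.80.
- For small interactions sample size is the main limit. With i = +0.25σ, mains 0.5σ and n = 75, V = 0.266 and k = 1.125; power is 0.13 against 0.19.
- The sizes and powers in Steps 3 and 4 are at unadjusted 0.05, whereas the SAP decides after Benjamini-Hochberg. Step 5 shows that the loss survives the adjustment.
- With no power calculation, a null interaction result would be weak evidence in any case. The shuffle makes it weaker.
- Freedman-Lane remains somewhat conservative when THC response varies, though less so than the SAP shuffle. Sign-flipping holds about 5% there but needs complete subjects. Neither was shown to hold 5% with varying response and incomplete subjects together.
- The SAP does not say that the phases are pooled, so Step 6 is conditional. The shift it describes arises only when ethanol has an effect, so it cannot produce a false ETOH finding.

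**Conclusion.** The concern holds. As written, the SAP tests the interaction, and each drug, against the hypothesis that no condition differs. For complete Phase 2B subjects with no true interaction, the null SD is inflated by √(1 + (a² + b²)/(3σ²)) at any sample size. The direction is always conservative in the cases examined.

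The power loss is negligible when drug effects are small, or when the interaction is sub-additive with moderate main effects. It is large, about 30 points or more in the cases above, when the interaction is synergistic and both main effects are near 1 residual SD. All effect sizes, the residual SD and the number of complete subjects are assumptions, and the documents do not show where this trial falls. The point should be fixed because the interaction is Phase 2B's stated question and a better-matched resampling test is available at little cost.

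**What to change.** Replace the single null with one specific to each contrast. For each coefficient:

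1. Fit the model without that term.
2. Shuffle the visit-level (pre, post) residual pairs within subject and phase.
3. Add back the reduced-model fit, refit the full model and compare the coefficient (Freedman-Lane).

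For the interaction in complete subjects, sign-flipping each subject's visit-adjusted contrast is an alternative, and the better calibrated one if THC response varies between subjects. Keep the full-label shuffle as a global test that no condition differs.

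Do not simply fall back on the plain mixed-model t or likelihood-ratio test unless it allows different residual variances before and after dosing. With post-dose variance assumed 2 or 3 times pre-dose, its simulated interaction size was 0.09 or 0.10, against 0.049 or 0.052 for Freedman-Lane and 0.048 in both cases for sign-flipping. That would defeat the SAP's stated aim of robustness.

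The cost is a few sentences in the SAP and a small change to the resampling code, with no new data. The Sample Size Determination section describes scan collection in the past tense, so the change should be dated, its reason stated, and the full-shuffle result reported alongside it.

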Driving Simulation: During this phase, we will use a computer-programmed driving simulator to assess motor coordination of the participants. The simulation will be programmed in STISIM on the computer and will be administered by a trained research coordinator. Subjects will be trained on this task during the screening task during the screening visit and given a refresher training on the task before testing. The task is performed on a laptop with the use of the keyboard, a joystick, and a foot pedal.

Participants perform tasks where they must center an object on the screen using the joystick, in addition to identifying numbers with the tap of the foot pedal.

Participants: 200 healthy, weekly or greater MJ users, aged 18-55, will be enrolled. Participants must test positive for cannabis and have no serious unstable medical illness to participate in the Phase II (See Participant Selection Section).

Phase 2B. *Examine potential interaction following co-administration of THC with oral ethanol exposure in healthy volunteers.*

[Design adapted from recently published alcohol interaction studies (Modi et al., 2007; Trevisan et al., 2008).]

Phase 2B is a randomized, double-blind, 4-treatment, 4-period, crossover study with THC or placebo administration and ethanol or placebo administration. On each of the 4 study days, participants will be admitted to the Translational and Clinical Research Center (TCRC) at Massachusetts General Hospital or the Center for Addiction Medicine (CAM). All visits in the TCRC and CAM will be monitored by licensed nursing staff. We will provide a breakfast of approximately 400 calories (e.g. juice, cereal, bagel), before study procedures begin.

[figure not shown]
Participants will be assigned randomly to 1 of 4 sequences, and receive each of the following treatments:

- Placebo THC + Ethanol
- THC + Placebo Ethanol
- THC + Ethanol
- Placebo THC + Placebo Ethanol

We will ensure a washout of at least 1 week between periods.

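### The SAP's shuffle test draws on all 24 visit orders although Phase 2B randomises to only 4 sequences, so its 5% level rests on an unjustified assumption that a participant's visits are exchangeable

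*SAP*

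**What the plan says.** The protocol (Study Procedures, Phase 2B) states: "Phase 2B is a randomized, double-blind, 4-treatment, 4-period, crossover study". On allocation it adds: "Participants will be assigned randomly to 1 of 4 sequences". The text does not list the four sequences; they may be in a figure that is not reproduced. Periods are separated by a washout of one week or more.

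The SAP (Statistical Model) fits a "multi-level linear regression model with subject-varying intercepts estimated via maximum likelihood". Under Covariates, "we will include covariates adjusting for visit order": three terms, shared by pre-dose and post-dose scans. Significance comes from shuffling. Each participant's completed conditions "will be randomly shuffled across their set of visits", the model is refitted, and "the prior two steps will be repeated 10,000 times". The observed coefficient is compared in absolute value with the shuffled ones, so the test is two-sided. There are three contrasts (THC, ETOH and their interaction) for each of two outcomes. "The total set of 6 p-values will be adjusted for multiple comparisons using the Benjamini-Hochberg method". The decision rule is: "An adjusted p-value < 0.05 will indicate a statistically significant effect".

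The SAP calls this a bootstrap, chosen for robustness. In substance it is a permutation test, and step 1 does not limit the shuffle to the randomised sequences.

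**The concern.** Randomisation by itself guarantees the level of a permutation test only when the test draws from the orders that could have been assigned. Here a four-visit completer can be shuffled into 4! = 24 orders, of which 24 - 4 = 20 were never possible. The test must then rely on exchangeability: apart from effects common to everyone, any two visits of the same person must be correlated to the same degree.

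Two ordinary features of repeated visits break this. Neighbouring visits may be more alike than distant ones, or individuals may drift at their own rates. A random intercept and common visit terms absorb neither. Four fixed sequences then place the conditions at spacings that differ from the average over 24 orders, and the shuffled coefficients have the wrong spread. All six primary p-values use this reference distribution, including the THC x ETOH interaction that serves Aim 3. The test could be too liberal, or too conservative and so lose power.

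**Working it through.** **Inputs from the documents.** Four treatments, four periods and 4 sequences (protocol, Phase 2B); an unrestricted within-person shuffle, Table 1 contrasts and a two-sided level of 0.05 (SAP, Statistical Model).

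**Assumptions.** The 4 sequences form a Latin square and are equally used; data are complete; no drug has any effect; the level is taken per test before Benjamini-Hochberg. The documents give no visit correlation, so several structures are tried.

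**Formula.** With complete data the interaction coefficient is the contrast placebo - THC - ETOH + both, taken over the post-dose scans. Let R be the contrast's variance averaged over the 4 sequences, divided by its variance averaged over the 24 orders. In large samples the true size is 2 x (1 - Phi(1.96/sqrt(R))).

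**Interaction by hand.** Over the four visits the contrast's signs follow one of three patterns (up to reversal), each produced by 8 of the 24 orders. Unit variance is used throughout. For AR(1) with correlation 0.5 the variance is 4 + 2(0.5 L1 + 0.25 L2 + 0.125 L3), where Lk sums the sign products at lag k. The next column adds equal independent noise (+4), so that half the variance is independent. For drift with SD 0.5 residual SD per visit, the variance is 4 + 0.25 x (sum of sign x time)^2, with time -1.5, -0.5, 0.5, 1.5.

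| Pattern | L1, L2, L3 | AR(1) 0.5 | Half independent | Drift |
|---|---|---|---|---|
| + + - - | 1, -2, -1 | 3.75 | 7.75 | 8 |
| + - + - | -3, 2, -1 | 1.75 | 5.75 | 5 |
| + - - + | -1, -2, 1 | 2.25 | 6.25 | 4 |
| Mean over 24 orders | | 2.583 | 6.583 | 5.667 |

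**Plan's own figure first.** With exchangeable visits only L1 + L2 + L3 matters. It is -2 in every row, so R = 1 and the size is exactly 5.0%.

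**AR(1) 0.5.** A square whose sequences all show + + - - has R = 3.75/2.583 = 1.452 and size 10.4%. One with only + - + - has R = 1.75/2.583 = 0.677 and size 1.7%. The 6 carryover-balanced squares either use only + - - + (R = 2.25/2.583 = 0.871, size 3.6%) or split evenly between the other two patterns (R = 2.75/2.583 = 1.065, size 5.7%).

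**All 24 Latin squares, true size at nominal 5%:**

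| Structure | Interaction | Interaction, balanced squares | Main effects |
|---|---|---|---|
| Exchangeable | 5.0% | 5.0% | 5.0% |
| AR(1) 0.5, no independent noise | 1.7-10.4% | 3.6% or 5.7% | 2.6-6.9% |
| AR(1) 0.5, half independent | 3.6-7.1% | 4.4% or 5.3% | 4.0-5.7% |
| Drift SD 0.5 per visit | 2.0-9.9% | 2.0% or 6.7% | 2.8-6.7% |

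In the second row the median interaction size is 4.7%, and 4 of the 24 squares exceed 7%.

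**No choice of four sequences matches all lags.** Over 24 orders the mean product of the first-visit and last-visit signs is (-1 - 1 + 1)/3 = -1/3. Four equally used sequences can give only multiples of 1/2.

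**Simulation of the SAP test** (100 completers, 2,500 null trials, 1,000 shuffles each). Exchangeable visits gave 4.6-5.7%. A mean drift common to everyone and both scans gave 4.4-5.6%, so the visit terms do remove it. With strong individual drift (SD 1.0), two labellings of a carryover-balanced square gave interaction sizes of 8.7% and 0.1%. Drawing only from the 4 sequences gave 4.9% and 4.7% on the same designs. Over all restricted runs the interaction size was 4.7-5.3% and main effects 4.5-6.2% (Monte Carlo standard error about 0.4 points).

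**The case against.** The strongest defence is that nothing is wrong under the SAP's own model. A random intercept with common visit effects implies exchangeable visits, and then the test is exact. That stands, and it makes the concern conditional.

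The wide ranges also reflect not knowing which sequences were used. A carryover-balanced square is a common choice, and with AR(1) 0.3 its interaction size is 4.4-5.3%, which is of no practical importance. That stands too, although individual drift still moves a balanced square to 2.0% or 6.7%.

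A reader might infer that the trial's false-positive rate is doubled. The documents do not support that. The figure of 10.4% is the worst of 24 squares under one assumed correlation with no independent scan noise, the error can equally be conservative, and the effect after the Benjamini-Hochberg step has not been calculated. A reader might also infer that any drift over the visits spoils the test; drift common to all participants and both scans is already adjusted for. Nor is the interaction always the contrast worst affected: in some squares one main effect is inflated just as much.

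There is also a fair objection to permuting sequence labels among all participants, because someone with missing visits could be given conditions that they did not complete. In a simulation with exchangeable visits, 60 participants, a balanced square, and assumed missing visits of 30% (THC) and 50% (THC + ETOH), that approach gave sizes of 3.8%, 2.7% and 6.5% for THC, ETOH and interaction. The SAP's shuffle gave 5.1%, 4.8% and 5.1% (standard error about 0.5 points). This limits the remedy to completers. It does not answer the mismatch itself.

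**Conclusion.** The mismatch is real and does not depend on which four sequences were used: the shuffle is unrestricted and the randomisation is not. The 5% level therefore rests on exchangeable visits, which the plan neither states nor defends, although it chose the procedure for robustness.

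How much this matters in this trial cannot be determined from the documents, and neither can its direction. Under the stated assumptions, the interaction test's size lies between 1.7% and 10.4% for AR(1) 0.5, narrowing to 3.6-7.1% when half the variance is independent. With moderate individual drift it is 2.0-9.9%. Near-nominal results are typical of balanced squares with weak serial correlation, and exchangeable visits give no error at all. Two-visit Phase 2A participants are unaffected, because both of their possible orders were randomised.

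The point is a conditional loss of protection that can be largely restored at little cost. It does not show that the primary p-values are wrong.

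**What to change.** List the four Phase 2B sequences in the SAP. Change step 1 of the procedure so that, in each of the 10,000 repetitions, the assigned sequence labels are permuted among participants with four complete visits, within any randomisation block. Keep the present within-person shuffle of completed conditions for Phase 2B participants with missing visits and for Phase 2A participants, so that everyone's observed set of conditions is preserved. The model, the contrasts and the Benjamini-Hochberg adjustment stay as written. Report the present shuffle as a sensitivity analysis.

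The cost is a sentence or two in the SAP and a few lines of code, using sequence assignments that the study already holds. The remaining weakness is that incomplete Phase 2B participants still rely on exchangeable visits. The SAP should say so and report how many there are.
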